### **Statistical Analysis Content**

### **Trial Completion Status**

List the total and per-center numbers and proportions of screened subjects, screening failures, and the reasons for screening failures.

Calculate the numbers and proportions of subjects enrolled, who completed the trial, and who withdrew early, including reasons for withdrawal.

Summarize protocol deviations according to the type and severity.

Provide a detailed subject population breakdown in tabular form.

Present a subject disposition flowchart, including detailed reasons for screening failures.

## **Baseline Data**

Baseline data analysis will be conducted based on the FAS.

Descriptive statistical analysis will be performed on medical history and general information, symptoms and physical examination, laboratory tests, electrocardiogram, and imaging indicators.

## **Primary Endpoint Analysis**

Analysis of the primary endpoint will be based on both FAS and PPS.

The primary efficacy endpoint of this study is the incidence of composite events, and a superiority test will be used.

Hypotheses for test ① are as follows:

Null hypothesis:  $T_1 - C \geq 0$

Alternative hypothesis:  $T_1 - C < 0$

Where  $T_1$  is the incidence of composite events in Experimental Group 1, and  $C$  is that in the control group. The difference in composite event rates between the two groups and the 95% confidence interval will be calculated. If the upper limit of the 95% confidence interval is less than 0, superiority is established.

Hypotheses for test ② are as follows:

Null hypothesis:  $T_1 - T_2 \geq 0.05$

Alternative hypothesis:  $T_1 - T_2 < 0.05$

Where  $T_1$  is the incidence of composite events in Experimental Group 1, and  $T_2$  is the incidence in Experimental Group 2. The difference and 95% confidence interval

between the two groups will be calculated. If the upper limit of the 95% confidence interval is less than 0.05, non-inferiority is established.

Testing will follow the fixed sequence of ①→②; if the previous hypothesis test is met, the subsequent comparison will be performed; otherwise, further comparison will be stopped.

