## STUDY DESIGN

### Summary

The study is a multicenter, three-arm, open-label, randomized, parallel-controlled trial, which plans to enroll 306 participants diagnosed with ATAAD from 7 hospitals in China. All patients receive TAR + FET procedure and are randomized to Group 1 (arch-clamping technique under mild hypothermia), Group 2 (arch-clamping technique under moderate hypothermia) and Group 3 (Sun's procedure using bilateral antegrade cerebral perfusion) in the ratio of 1:1:1. After a 1-year follow-up, the validity and safety of the mild hypothermic arch-clamping technique for ATAAD is

evaluated via the incidence of major adverse events including death, renal replacement therapy (RRT), stroke, and paraplegia, as well as times of circulatory arrest, cardiopulmonary bypass, and mechanical ventilation, and length of stay.

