## **Rationale for Study Design**

- (1) Prospective: Prospective design minimizes bias. Standardized enrollment criteria, methods, process, and outcome measures, clarify the causal relationship.
- (2) Multicenter: Multicenter trials can enroll participants rapidly, resulting in shorter clinical trial periods, good extrapolation, and minimal bias caused by systematic errors.
- (3) Three-arm: This study involves two technical optimizations: temperature change from moderate temperature to mild temperature; unilateral antegrade cerebral perfusion changed to bACP. Due to the inability to control two variables simultaneously using a two-arm design, we plan to establish three groups for a randomized controlled trial.
- (4) Randomized: This trial uses randomization at each center. Each participant successfully screened has equal opportunity and is randomly assigned to Group 1 (arch-clamping technique under mild hypothermia), Group 2 (arch-clamping technique under moderate hypothermia) and Group 3 (Sun's procedure using bilateral antegrade cerebral perfusion) in a 1:1:1 ratio without the investigator nor the participant's personal preferences influence.
- (5) Open-label: The three surgical procedures differ significantly in terms of manipulation, so it is impossible to blind the researchers and participants.
- (6) Parallel-controlled: Sun's procedure as a TAR+FET technique, is the standard surgical treatment for ATAAD.

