## Measures to Control Bias

(1) Prospective study design: Subjects and study methods are determined prior to the start of the trial, with all relevant confounding factors included in the statistical analysis. Strict quality control is maintained throughout the study, and all cases that meet the design criteria are included in the final analysis. This approach yields higher-quality and more reliable clinical data and avoids the selection and data processing bias associated with retrospective studies.

(2) Multicenter design: Considering differences in geographic region, hospital, or physician expertise, multicenter case samples are more representative than those from a single center. In addition, multicenter design helps prevent systematic errors from a single center that could bias study results, thereby increasing the credibility of the conclusions. To minimize inter-center variability, all study-related personnel at each center will receive standardized training.

(3) Investigator training: Prior to study initiation, the principal investigators at each center will provide training on the study protocol to ensure that all investigators

are familiar with and understand the surgical procedures for each group.

(4) Standardized application of inclusion and exclusion criteria: Subjects will be screened strictly according to the protocol's inclusion and exclusion criteria, minimizing selection bias.

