## Statistical Considerations

### Sample Size

#### Estimation of Total Sample Size

Sample size estimation is performed using PASS 2021 software.

This study adopts a superiority design and a fixed sequence testing strategy. The primary outcome is the incidence of composite events, which is a low-benefit endpoint. The hypotheses are as follows:

- ① Experimental Group 1 is superior to the control group.
- ② Experimental Group 1 is non-inferior to Experimental Group.

The order of hypothesis testing is ①→②. According to the *Guideline on Multiplicity in Clinical Drug Trials*, this strategy will not inflate the overall Type I error rate (FWER), and no adjustment for multiplicity is required.

Based on previous research, the incidence of composite events with mild hypothermic aortic arch clamping combined with bilateral cerebral perfusion is approximately 13.64%, with moderate hypothermic arch clamping combined with unilateral cerebral perfusion is approximately 22.67%, and with the traditional Sun's procedure is approximately 29.63%.

For hypothesis ①, assuming the composite event rate is 13% in Experimental Group 1 and 30% in the control group, with a superiority margin set at 0, a one-sided significance level of 0.025, a power of 80%, and an allocation ratio of 1:1, at least 91 subjects are required in each group.

For hypothesis ②, assuming the composite event rate is 25% in Experimental Group 2 with a non-inferiority margin of 5%, at a one-sided significance level of 0.025, a power of 80%, and an allocation ratio of 1:1, at least 84 subjects are required

in each group.

In summary, taking the maximum required sample size above and allocating subjects in a 1:1:1 ratio among the three groups, and accounting for a 10% dropout rate, a total of 306 subjects will be enrolled in this study, with 102 subjects in each group.

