## **Sample Size Allocation and Determination**

This study will be conducted simultaneously in multiple clinical centers. In principle, the number of subjects enrolled per center will be distributed as evenly as possible to ensure adequate center representation. However, considering feasibility and the pace of enrollment, the number of subjects recruited at each participating site may be adjusted to ensure enrollment balance among centers. In any case, the final enrollment at a single center should not exceed 50% of the total sample size.

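### Both primary tests use a crude rate difference with no centre term, although patients are randomised at each of 7 centres and the protocol says relevant confounders are in the analysis

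*Combined protocol and SAP*

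**What the plan says.** Primary Endpoint Analysis defines test 1 (Experimental Group 1 against control) by a crude difference: "The difference in composite event rates between the two groups and the 95% confidence interval will be calculated". Superiority needs an upper limit below 0. Test 2 (Group 1 against Group 2) has the same form and needs an upper limit below 0.05. No method for the interval is named.

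General Principles, under Statistical Methods, gives chi-square or Fisher for qualitative data and keeps Cochran-Mantel-Haenszel for multi-category and ordered data, with no stratification factor. Secondary Endpoint Analysis refers back to those principles.

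On design, the Summary section "plans to enroll 306 participants diagnosed with ATAAD from 7 hospitals in China". Rationale for Study Design, item (4), says "This trial uses randomization at each center" and "Each participant successfully screened has equal opportunity and is randomly assigned"; it does not say whether lists are blocked within centre. Sample Size Allocation and Determination requires only that "the final enrollment at a single center should not exceed 50% of the total sample size".

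Measures to Control Bias, item (1), describes the trial as run "with all relevant confounding factors included in the statistical analysis", naming no factor. Item (2) begins "Considering differences in geographic region, hospital, or physician expertise, multicenter case samples are more representative".

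**The concern.** The bias-control section describes an analysis that includes relevant factors, and the analysis section includes none. In an open-label trial that leaves room for dispute. A crude result, or one adjusted for factors chosen later, could each be presented as following the protocol.

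The primary analysis also ignores the units within which patients are randomised, although the protocol expects hospitals and surgeons to differ and one centre may supply half the patients. If allocation is balanced within centre and centres differ in risk, the crude standard error includes between-centre spread that the balance has already removed from the estimate. The interval is then too wide and the test conservative. If simple randomisation is used at each centre, the crude interval has about its nominal coverage. The documents do not say which applies.

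**Working it through.** **1. The plan's own figure.** From Estimation of Total Sample Size: "assuming the composite event rate is 13% in Experimental Group 1 and 30% in the control group", one-sided 0.025, power 80%, 1:1. With pooled variance under the null:

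n = [1.96 × √(2 × 0.215 × 0.785) + 0.8416 × √(0.13 × 0.87 + 0.30 × 0.70)]² / 0.17² = (1.139 + 0.478)² / 0.0289 ≈ 90.5, so 91 per group.

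91 / 0.90 = 101.1, so 102 per group, and 3 × 102 = 306. Both stated figures reproduce, with no centre term in the calculation.

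**2. The two estimators.**
- Crude: d = p1 − p0, SE² = p1(1 − p1)/n1 + p0(1 − p0)/n0 (Wald interval; this is an assumption, because the plan names no method).
- Centre-stratified (Mantel-Haenszel): d_MH = Σ w_k(p1k − p0k) / Σ w_k, with w_k = n1k·n0k/(n1k + n0k), and Sato's variance.

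If the arms are equal in size within every centre, w_k is proportional to centre size and the two point estimates are identical. Only the interval width differs.

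**3. Assumptions not in the documents.** 7 centres; per-arm sizes 37, 9, 9, 9, 9, 9, 9 (largest 37/91, about 40%); centre effects normal on the log-odds scale with SD 0, 0.5, 0.8 or 1.0; overall rates held at 13% and 30%; 91 per arm. Each setting was simulated 400,000 times, so the simulation error on a power near 82% is √(0.82 × 0.18/400,000), about 0.06 point.

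**4. Test 1 power, crude vs stratified (%).**

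| Centre SD | Balanced within centre | Simple randomisation at centre |
|---|---|---|
| 0 | 81.9 vs 81.7 | 81.4 vs 80.1 |
| 0.5 | 81.8 vs 82.4 | 81.2 vs 81.1 |
| 0.8 | 82.0 vs 83.8 | 80.9 vs 82.2 |
| 1.0 | 82.2 vs 84.8 | 80.8 vs 83.3 |

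For SD 0.5 to 1.0, changing the centre mix (largest centre about 50%, or all equal) gives gains of 0.6 to 2.8 points (balanced) or −0.2 to 3.0 points (simple).

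**5. Interval width, balanced.** The stratified/crude SE ratio is 1.000 / 0.986 / 0.967 / 0.951, so the crude interval is 0 / 1 / 3 / 5% wider.

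**6. Test 1 one-sided error (20% in both arms).**
- Balanced: crude 2.7 / 2.6 / 2.3 / 2.1%; stratified 2.6 to 2.7%.
- Simple randomisation: both 2.6 to 2.7%; crude coverage 94.7 to 94.8%.

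**7. Test 2 (13% vs 25%, margin 5 points, 91 per arm, balanced; 200,000 replicates).** Crude power is 84.6 / 85.1 / 85.7 / 86.4%; stratifying changes it by −0.1 / +0.7 / +1.6 / +2.4 points. At the margin (25% vs 20%, SD 0.5 to 1.0), stratified one-sided error is 2.6 to 2.7% if the risk difference is the same in every centre. If the odds ratio is the same instead, it is 2.8 to 3.1%, against 2.3 to 2.6% crude.

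**8. Cross-check.** A separate simulation with equal-sized, balanced centres (20,000 trials per setting) gave test 1 power of 82.0 vs 82.6% at SD 0.5 and 82.2 vs 85.1% at SD 1.0, with crude error falling to 2.0%.

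**The case against.** A crude risk difference is a valid analysis of a randomised trial, and nothing here threatens the planned power or the error rate. The gain, and even its sign, depends on an assumed between-centre SD. At SD 0.3, test 1 power is 81.7% crude vs 81.8% stratified (balanced), and 81.3 vs 80.5% (simple), so with little heterogeneity stratifying gains almost nothing or loses a little. At the non-inferiority margin, a constant odds ratio puts the stratified test slightly above 2.5%, where the crude test is near nominal or conservative. With 9 patients per arm, a small centre expects only about 9 × 0.13 = 1.2 Group 1 events. The confounder sentence is general language about prospective design and does not name centre; the same section answers inter-centre variability with standardised training.

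The points on size stand, and they are why this is a modest improvement and not a defect in validity. They do not remove the mismatch. The sentence on confounders concerns the statistical analysis, and no section carries it out. Training may reduce centre differences but does not account for those that remain. Mantel-Haenszel weighting tolerates sparse strata, and a pooling rule deals with the smallest centres.

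**Conclusion.** The concern holds. Neither primary test includes centre, no specified inferential analysis includes any covariate, and the bias-control section says otherwise. The consequence is small. Over an assumed centre log-odds SD of 0 to 1.0, stratifying changes test 1 power by −0.2 to +2.6 points if allocation is balanced within centre and by −1.3 to +2.5 points if it is not. With balance, the crude test becomes mildly conservative (error down to 2.1% at SD 1.0). Crude power stays above 80% in every test 1 setting tabulated, and is 85.7 to 85.9% if all 102 per arm are evaluable (balanced). These sizes rest on the assumed centre SD, the assumed centre sizes and a Wald interval for the crude comparison, none of which the documents give. It should be changed because the better-matched analysis costs little and fixes the primary estimator in advance.

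**What to change.** - **Primary Endpoint Analysis:** for both tests, make the centre-stratified risk difference primary (Mantel-Haenszel with a named variance, or stratified Miettinen-Nurminen), with its 95% interval and the existing limits of 0 and 0.05. Fix a rule for pooling small centres before database lock. Keep the crude difference as a sensitivity analysis, which also shows any divergence at the test 2 margin.
- **Measures to Control Bias, item (1):** name the factors actually included.
- **Rationale for Study Design, item (4):** state whether allocation is balanced within centre.

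**Cost:** one analysis sentence with its pooling rule and two matching edits. No new data are needed and the total of 306 does not change. If centres do not differ at all, stratifying costs about 0.2 point of test 1 power with balanced allocation and about 1.3 points with simple randomisation. With balanced allocation, test 2 one-sided error may reach 2.8 to 3.1% if the odds ratio, and not the risk difference, is constant across centres. Correcting only the confounder sentence would remove the contradiction but leave the efficiency unused.

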## Study-Related Assessments

### Medical History and General Information

- (1) Demographics: Age, sex, height, weight, body mass index (BMI), body surface area (BSA).
- (2) Medical History: History of hypertension, coronary artery disease and treatment, diabetes mellitus and treatment, neurological complications and treatment, chronic obstructive pulmonary disease, chronic renal failure and treatment, thyroid dysfunction, peripheral vascular disease, history of cirrhosis or gastrointestinal bleeding, family history of hereditary aortic diseases (Marfan syndrome, Loeys-Dietz

syndrome, vascular Ehlers-Danlos syndrome, familial thoracic aortic aneurysm and dissection, etc).

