## Preoperative Laboratorial Tests

(1) Complete blood count: Hemoglobin, white blood cell count, neutrophil count, neutrophil percentage, C-reactive protein, platelet count;

(2) Biomarkers of coagulation function: D-dimer, fibrinogen;

(3) Biomarkers of myocardial injury: Myoglobin, troponin, creatine kinase-MB, creatine kinase, lactate dehydrogenase, B-type natriuretic peptide;

(4) Biomarkers of liver function: Albumin, alanine aminotransferase, aspartate aminotransferase, total bilirubin, direct bilirubin.

(5) Biomarkers of renal function: Serum creatinine, creatinine clearance rate, uric acid, cystatin C;

(6) Arterial blood gas analysis: PaO2, PaCO2, arterial oxygen saturation, arterial potassium, arterial lactate.

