#### **Visit 1: Emergency Admission**

- (1) Obtain signed informed consent from the subject.

- (2) Collect medical history and general information.
- (3) Collect symptoms and physical examination findings.
- (4) Collect laboratory tests including complete blood count, liver and renal function, etc.
- (5) Collect ECG and imaging data.
- (6) Verify inclusion and exclusion criteria. Eligible subjects are enrolled and assigned a randomization number, and randomized to Experimental Group 1, Experimental Group 2, or Control Group.

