## **Statistical Methods**

### **General Principles**

(1) Descriptive statistics: For quantitative variables, the number of cases, mean, standard deviation, median, interquartile range, minimum, and maximum values will be reported. For qualitative variables, absolute and relative frequencies will be reported.

(2) Inferential statistics: Unless otherwise specified, two-sided tests will be used, and a two-sided P-value less than or equal to 0.05 will be considered statistically significant. Comparisons of quantitative data between groups will be performed by analysis of variance or rank-sum test; comparisons of qualitative data will use the chi-square test or Fisher's exact test; multicategorical or ordinal data will be analyzed using the Cochran-Mantel-Haenszel (CMH) test.

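### Both primary tests use a crude rate difference although age and preoperative creatinine are planned at Visit 1; a prespecified adjusted risk difference would probably be somewhat more efficient, at almost no cost

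*Combined protocol and SAP*

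**What the plan says.** All references are to the combined protocol and SAP.

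- **Primary Endpoint Analysis.** For test 1 (Experimental Group 1 against control): "The difference in composite event rates between the two groups and the 95% confidence interval will be calculated". Superiority requires an upper limit below 0. For test 2 (Experimental Group 1 against Experimental Group 2): "If the upper limit of the 95% confidence interval is less than 0.05, non-inferiority is established". Test 2 is done only if test 1 succeeds.
- **General Principles.** The default for binary data is unadjusted: "comparisons of qualitative data will use the chi-square test or Fisher's exact test".
- **Baseline Data.** "Descriptive statistical analysis will be performed on medical history and general information, symptoms and physical examination, laboratory tests, electrocardiogram, and imaging indicators". No other use of these values is given.
- **Preoperative Laboratorial Tests.** The list includes "Biomarkers of renal function: Serum creatinine, creatinine clearance rate, uric acid, cystatin C" and, under blood gases, "arterial oxygen saturation, arterial potassium, arterial lactate". Age is recorded under Medical History and General Information.
- **Visit 1: Emergency Admission.** "Collect laboratory tests including complete blood count, liver and renal function, etc" is listed ahead of the eligibility check and randomisation. The Study Flowchart has a row for renal function but none for blood gases.
- **Measures to Control Bias.** The first item says that the confounders that matter will be taken into account in the analysis. It gives no list and no model.
- **Handling of Missing and Abnormal Values.** Imputation of missing data is ruled out.

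**The concern.** The composite counts death, renal replacement therapy, stroke and paraplegia. Preoperative creatinine is a plausible predictor of renal replacement therapy, and age and lactate are plausible predictors of death. A comparison that ignores them leaves their chance imbalance in the random error of the difference. Adjustment by standardisation takes out part of that error while keeping the same risk difference, hypotheses, margins and test order.

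The trial is sized at about 80% power for test 1, and a near miss there also closes test 2, so a few points of power matter.

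There is also a gap in the text. Measures to Control Bias commits to including confounders, while the analysis sections include none. If this stays open, covariates could be picked after outcomes are known by arm, in an open-label trial.

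**Working it through.** **1. The plan's own figures.** The inputs come from Estimation of Total Sample Size: 13% against 30% for test 1, 13% against 25% with a 5-point margin for test 2, one-sided 0.025, 80% power, 10% dropout.

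Test 1, pooled variance under the null, mean rate 0.215:

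n = [1.960·√(2·0.215·0.785) + 0.842·√(0.13·0.87 + 0.30·0.70)]² / 0.17² = 90.5, so 91. Then 91/0.9 = 101.1, so 102, and 3 × 102 = 306. This matches the plan. Power at 91 per arm is 80.2%.

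Test 2, distance 0.25 - 0.13 + 0.05 = 0.17: the unpooled form gives 81.6, the pooled form 83.005 (84 when rounded up) and Farrington-Manning 84.6. The stated 84 is reproduced. Both figures are for crude comparisons.

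**2. What a variance reduction is worth.** Let VR be the share of the variance removed by adjustment. With v = 0.3231 (test 1) or 0.3006 (test 2), power = Φ(0.17/√[(1 - VR)·v/91] - 1.96), and the equivalent crude sample is 91/(1 - VR).

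| VR | Test 1 power | Test 2 power | Equivalent n per arm |
|---|---|---|---|
| 0 | 81.4% | 84.1% | 91.0 |
| 5% | 83.3% | 85.9% | 95.8 |
| 10% | 85.3% | 87.7% | 101.1 |
| 20% | 89.1% | 91.1% | 113.8 |

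The 81.4% differs from 80.2% only because this formula uses the unpooled variance.

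**3. How large VR could be.** The documents give no prognostic strength, so the AUC of the covariates for the composite is an assumption, run over a range. Simulation: 91 per arm, 5000 trials per setting, logistic model with arm and four baseline covariates, standardised risk difference with influence-function standard error. Monte Carlo error is about 0.5 points of power.

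| Assumed AUC | Test 1, crude to adjusted | VR | Test 2, crude to adjusted | VR |
|---|---|---|---|---|
| 0.50 | 80.6% to 79.6% | -2% | 85.0% to 84.2% | -3% |
| 0.63 | 82.5% to 82.8% | 1% | 85.4% to 85.5% | 1% |
| 0.70 | 81.6% to 84.2% | 6% | 83.6% to 86.8% | 7% |
| 0.76 | 81.9% to 87.2% | 13% | 83.9% to 89.3% | 14% |
| 0.82 | 82.0% to 90.2% | 22% | 84.6% to 92.4% | 22% |

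Two further simulations agree. A single risk score gave 0 to 1 point at AUC 0.63, 2 to 3 at 0.69 and 4 to 5 at 0.74. Three separate covariates gave -1 to 0 points with no prognostic value, and +1, +2 to 3 and +4 at logit slopes of 0.5, 0.75 and 1.0.

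**4. Cross-check by hand, test 2, slope 0.75 per SD (AUC about 0.69).** The standard error of a standardised baseline difference is √(2/91) = 0.148 SD. A one-standard-error imbalance moves the crude difference by at most 0.75 × 0.148 × (0.1131 + 0.1875)/2 = 1.7 points, and by about 1.5 after averaging over the score. The standard error of the crude difference is √(0.3006/91) = 5.7 points. The share of variance is (1.5/5.7)², about 7%, in line with the table.

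**5. Type I error.** The null settings were 30% in both arms for test 1, and 25% against 20% with the 5-point margin for test 2. One-sided error was 2.3 to 2.9% crude and 2.5 to 3.0% adjusted with four covariates. With three covariates it was 2.9 to 3.0% crude and 2.6 to 2.9% adjusted.

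**6. Events available.** Test 1: 91 × (0.13 + 0.30) = 39. Test 2: 91 × (0.13 + 0.25) = 35. Arm plus three covariates is four coefficients, which is about as far as these counts should be stretched.

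**The case against.** The strongest reply is that nothing needs correcting. A randomised comparison of two proportions with a 95% interval is a standard analysis, and it reaches the plan's power target unadjusted. That stands: this is an improvement in efficiency and does not repair an error.

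The second reply is that the benefit is assumed. That stands too. If the covariates carry no information, precision gets slightly worse. No baseline biomarker is an obvious predictor of stroke or paraplegia, and the exclusion of chronic renal failure may narrow the creatinine range.

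The third reply is that Measures to Control Bias already covers confounders. It does not make the primary test adjusted, because it names neither a covariate nor a model and nothing in the analysis sections carries it out.

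A reader might also infer more than the documents support:

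- **That chance imbalance biases the crude result.** It does not. It is random error, already covered by the unadjusted interval.
- **That adjustment is certain to narrow the interval.** That depends on a prognostic strength the documents do not give.
- **That lactate will be available in every patient.** It is in the preoperative list, but the flowchart has no blood-gas row and Visit 1 does not name it.

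**Conclusion.** The point holds as one of efficiency. The primary analysis leaves planned baseline information unused, and the plan's general statement on confounders is not carried into its analysis sections.

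The expected change in power at 91 evaluable patients per arm is about -1 to 0 points if the covariates are useless, 0 to 1 at AUC about 0.63, 2 to 3 at about 0.70 and 4 to 5 at about 0.75. An AUC of 0.82 would give about 8 points, but the documents offer no reason to plan on that. These figures rest on the plan's event rates, the assumed AUC and complete covariates. The validity of the crude test and the 306 total are not in question.

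**What to change.** 1. In Primary Endpoint Analysis, make the primary estimate of T1 - C and of T1 - T2 the standardised (marginal) risk difference from a logistic model with arm plus a short covariate list, in both FAS and PPS. Use a robust 95% interval against the same limits of 0 and 0.05, in the same test order. Keep the crude difference as a supporting analysis.
2. Fix the list before any outcome data are compared by arm: age and log creatinine, plus log arterial lactate only if its completeness is confirmed. Use values taken before randomisation.
3. In Handling of Missing and Abnormal Values, add an explicit exception that allows a simple fill-in rule for missing baseline covariates. Without it, patients with a missing covariate would drop out of the primary analysis.
4. Align Measures to Control Bias and Baseline Data with this, so that all three sections name the same covariates.

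The cost is a few sentences in the plan and a few lines of code. No new data item is needed, and the sample size, margins and hypotheses do not change. The downside is that the list must be prespecified and short, given 35 to 39 events per comparison, with a very small loss of precision if the covariates turn out not to be prognostic.
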